### **11.1.2 Serious Adverse Event**

A serious adverse event (SAE) is any experience that suggests a significant hazard, contraindication, side effect or precaution. It is any AE that results in any of the following outcomes:

1. Death
2. A life-threatening adverse event
3. Inpatient hospitalization or prolongation of existing hospitalization
4. A persistent or significant disability or incapacity
5. A congenital anomaly/birth defect in the offspring of a participant who received the study treatment

Important medical events that may not be immediately life-threatening or result in death or hospitalization but may jeopardize the participant or may require intervention to prevent one of the outcomes listed above. Examples of such events are intensive treatment in an emergency room or at home for allergic bronchospasm; blood dyscrasias or convulsions that do not result in hospitalization; or the development of drug dependency or drug abuse.

### **11.1.3 Unexpected Adverse Reaction**

An unexpected adverse reaction is an adverse reaction, the nature and severity of which is not consistent with the applicable product information (e.g., Investigator's Brochure for an unapproved investigational product or package insert/summary of product characteristics for an approved product).

### **11.1.4 Laboratory Test Abnormalities**

The investigator must assess the clinical significance of all abnormal laboratory values as defined by the compendium of normal values for the reference laboratory.

Protocol 20BWHM:

A randomized, double-blind, placebo-controlled study to investigate the effects of a *Bifidobacterium breve* strain on fat loss in healthy adults

Any treatment emergent abnormal laboratory result which is clinically significant, i.e., meeting one or more of the following conditions, should be recorded as a single diagnosis on the AEs form in the study record:

1. Accompanied by clinical symptoms
2. Leading to interruption or discontinuation of the investigational product
3. Requiring a change in concomitant therapy

This applies to any protocol and non-protocol specified laboratory result from tests performed after the first dose of the investigational product, which falls outside the laboratory reference range and meets the clinical significance criteria for liver and kidney tests as well as for hematology and clinical chemistry, etc. (i.e. AST and/or ALT > 2 x ULN).

This does not apply to any abnormal laboratory result which falls outside the laboratory reference range but which does not meet the clinical significance criteria or those which are a result of an AE which has already been reported.

Any laboratory result abnormality fulfilling the criteria for a serious adverse event (SAE) should be reported as such, in addition to being reported as an AE in the study record.

## **11.2 Treatment and Follow-Up Of AEs And Laboratory Abnormalities**

### **11.2.1 Treatment and Follow-up of AEs**

AEs, especially those for which the relationship to the investigational product is suspected, should be followed up until they have returned to baseline status or stabilized.

If after follow-up, return to baseline status or stabilization cannot be established, an explanation should be recorded in the study record.

### **11.2.2 Treatment and Follow-up of Laboratory Abnormalities**

In the event of participant-initiated withdrawal or clinically significant unexplained abnormal laboratory test values, the participant will be withdrawn from the treatment and will remain in the study and be required to attend all remaining study visits as part of a safety arm.

## **11.3 Reporting of SAEs And Unexpected Adverse Reactions**

The qualified investigator will be responsible for classification of an AE as an SAE within 24 hours of notification. Causality should be signed off by the qualified investigator prior to reporting to ethics and regulatory bodies. Notification of any serious adverse events must be made in writing to the study sponsor. The IRB will be notified of all product related SAEs and unexpected adverse reactions. All blinded SAE's or unblinded-participant-on-active product SAE's will be reported to the Therapeutics Products Directorate (TPD) in an expedited manner.

Protocol 20BWHM:

A randomized, double-blind, placebo-controlled study to investigate the effects of a *Bifidobacterium breve* strain on fat loss in healthy adults

KGK Science must notify the TPD of all blinded or unblinded-participant-on-active product serious adverse events and reactions as follows:

If it is neither fatal or life threatening, within 15 calendar days after the day on which the sponsor becomes aware of the information; and

If it is fatal or life threatening, must be reported as soon as possible, but not later than seven (7) days after the day on which the sponsor becomes aware of the information.

Protocol 20BWHM:

A randomized, double-blind, placebo-controlled study to investigate the effects of a *Bifidobacterium breve* strain on fat loss in healthy adults

## 12 STATISTICAL EVALUATION

### 12.1 Determination of Sample Size

With a total sample size of 100 (50 per group; 40 completers), it is possible to detect a difference in mean change in percent body fat or body fat mass of 0.76% or 0.79 kg respectively, in a parallel design at a two-sided unadjusted 5% significance level, 80% power and 20% attrition rate. This calculation is based on standard deviations of 1.19% and 1.24 kg for percent body fat and body fat mass respectively, estimated from a study by Minami et al (2018).

### 12.2 Analysis Plan

The **Safety Population** will consist of all participants who received any amount of either product, and on whom any post-randomization safety information is available.

The **Intent-to-Treat (ITT) Population** consists of all participants who received either product and on whom any post-randomization efficacy information is available.

The **Per Protocol (PP) Population** consists of all participants who consumed at least 80% of treatment or placebo doses, do not have any major protocol violations and complete all study visits and procedures connected with measurement of the primary variable.

### 12.3 Statistical Analysis Plan

For each continuous endpoint including percent body fat, body fat mass, visceral fat area, weight, BMI, total cholesterol, HDL-cholesterol, LDL-cholesterol, triglycerides, waist circumference, and hip circumference, fasting blood glucose, HbA1c, fasting insulin levels, AST, ALT, GGT, ALP, a summary table will be prepared with a variety of summary statistics including mean, standard deviation, median, min-max range and number of participants analyzed for each time point-treatment pairing. These data will be classified in subgroups based on the similarity of microbiota composition.

To account for any a priori differences between groups, the similar summary statistics of the changes from baseline will also be provided. Mean values will be displayed as graphs, with a separate line for each product, and error bars indicating  $\pm$  SEM. Mean changes from baseline will also be graphed similarly. Changes in continuous endpoints from screening/baseline will be calculated as:

$$\text{Change to } V_i = \text{Value at } V_i - \text{Value at } V_{\text{screening/baseline}}$$

Continuous variables will be tested for normality and log-normality using histograms, box plots and Q-Q plots. Log-normally distributed variables will be analyzed in the logarithmic domain. Summary statistics will be provided as non-transformed values. Intractably non-normal variables will be analyzed by appropriate non-parametric tests.

Protocol 20BWHM:

A randomized, double-blind, placebo-controlled study to investigate the effects of a *Bifidobacterium breve* strain on fat loss in healthy adults

The primary endpoint - change in fat loss from baseline (%) or g), as assessed by Dual-Energy X-Ray Absorptiometry (DXA), between *B. breve* and placebo after 12 weeks of supplementation - will be assessed for between-group differences using ANCOVA, with the baseline measurements as covariate.

Continuous secondary endpoints will be tested for between-group differences using repeated measures linear mixed-effects ANCOVA. This will allow for the random effects associated with each subject to be accounted for. The dependent variable will be the change at each visit, the fixed effects will be the study group \* visit number, and the covariate will be the dependant variable at baseline (Day 0).

Baseline values for continuous variables will be tested for between-group differences using the independent Student's t-test. Within-group differences will be assessed using the Student's paired t-test or, in the case of intractable non-normality, the Wilcoxon sign rank test. The frequency of BMs will be calculated as the average number of BMs per day over the 7 days prior to baseline and 7 days prior to week 6 and week 12.

For categorical variables, counts and percentages will be presented. The denominator for each percentage will be the number of subjects within the study group for that visit/week unless otherwise specified. Possible differences between groups will be assessed by using the two-tailed Chi-squared or Fisher's exact test, as appropriate.

Microbiota analysis will be performed at Morinaga Milk Co., Ltd. The subgroups will be determined based on the similarity of microbiota composition by hierarchical clustering. These subgroups will be defined before analyzing week 12 data.

All missing efficacy/effectiveness values analysis will be imputed using the most recent previously-available value (LOCF, or "last-observation-carried-forward" imputation) or multiple imputation. No imputation will be performed for missing values of safety variables.

All statistical analysis will be completed using R Statistical Software version 3.5.3 (R Core Team, 2019) for Microsoft Windows or SAS software, Copyright © 2019 SAS Institute Inc. SAS and all other SAS Institute Inc. product or service names are registered trademarks or trademarks of SAS Institute Inc., Cary, NC, USA.

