### 7.1 Inclusion Criteria

1. Male or female between 20 and 65 years of age, inclusive
2. BMI from 25.0 to 29.9 kg/m^2, inclusive
3. Female participants are not of child-bearing potential, defined as females who have undergone a sterilization procedure (e.g. hysterectomy, bilateral oophorectomy, bilateral tubal ligation, complete endometrial ablation) or have been post-menopausal (natural or surgically) for at least 1 year prior to screening

Or,

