## 5. EFFECTIVENESS/ EFFICACY ANALYSIS

### 5.1 Primary outcomes

Primary Outcomes	Hypothesis
1- The difference in change in fat loss from baseline (% or g), as assessed by DXA, between B. breve and placebo after 12 weeks of supplementation.	H0: There is no difference in mean change in fat loss, as assessed by DXA, from baseline at week 12 between B. breve and placebo

Summary statistics including number of participants, mean, median, standard deviation, minimum, and maximum will be obtained for baseline and week 12 visits. Similar summary statistics will be obtained for the change from baseline to week 12. Mean values will be displayed as graphs, with a separate line for each product, and error bars indicating  $\pm$  SEM. Mean changes from baseline will also be graphed similarly.

The primary outcome will be assessed using ANCOVA, with the baseline measurements as covariate and group as the factor variable. The dependent variable will be the change from baseline at week 12. Q-Q plots and residuals versus fitted values plots will be generated for the evaluation of the model adequacy. If the residual plots show violation of the model assumptions, log or other transformation of the dependent variable will be performed.

Between group differences will be assessed by two-sample t- test. If the outcome is not normally distributed, then Wilcoxon rank sum test will be used.

Within group differences will be assessed by paired t-test if the outcome is normally distributed and Wilcoxon signed rank test otherwise. P-values and 95% confidence intervals will be calculated.

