6. The difference in change from baseline between B. breve and placebo in the frequency of bowel movements after 6 and 12 weeks of supplementation	
H06.1:
 
There is no difference in mean change in the frequency of bowel movements from baseline at week 6 between B. breve and placebo
 
H06.2:
 
There is no difference in mean change in the frequency of bowel movements from baseline at week 12 between B. breve and placebo

Summary statistics including number of participants, mean, median, standard deviation, minimum, and maximum will be obtained for each visit. Similar summary statistics will be obtained for each available change from baseline to each subsequent visit. Mean values will be displayed as graphs, with a separate line for each product, and error bars indicating  $\pm$  SEM. Mean changes from baseline will also be graphed similarly.

Continuous secondary outcomes #2 and # 6 will be assessed using linear mixed effects ANCOVA, the fixed effects will include the baseline measurements as covariate and group\*visit as the factor variables. The dependent variable will be the change at each visit.

Continuous secondary outcomes #1, #3, #4, and #5 will be assessed using ANCOVA, with the baseline measurements as covariate and group as the factor variable. The dependent variable will be the change from baseline at week 12.

Q-Q plots and residuals versus fitted values plots will be generated for the evaluation of the model adequacy. If the residual plots show violation of the model assumptions, log or other transformation of the dependent variable will be performed.

Between group differences will be assessed by two-sample t- test. If the outcome is not normally distributed, then Wilcoxon rank sum test will be used.

Within group differences will be assessed by paired t-test if the outcome is normally distributed and Wilcoxon signed rank test otherwise. P-values and 95% confidence intervals will be calculated.

For categorical variables, counts and percentages will be presented. The denominator for each percentage will be the number of subjects within the study group for that visit/week unless otherwise specified. Possible differences between groups will be assessed by using the two-tailed Chi-squared or Fisher's exact test, as appropriate.

The frequency of BMs will be calculated as the average number of BMs per day over the 7 days prior to baseline and 7 days prior to week 6 and week 12.

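### The normality rules differ between protocol and SAP, and the only between-group rank test named leaves out the baseline covariate, so an adjusted analysis could be replaced or accompanied by an unadjusted one

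*Protocol*

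**What the plan says.** Protocol 12.3 puts the distributional check on the variables: "Continuous variables will be tested for normality and log-normality using histograms, box plots and Q-Q plots". Variables judged log-normal are analysed on the log scale. For what remains, "Intractably non-normal variables will be analyzed by appropriate non-parametric tests". It does not mention residuals, does not name the between-group rank test, and does not say whether baseline stays in. The primary analysis in the same section is an ANCOVA with baseline as covariate.

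SAP 5.1 and 5.2 fit the ANCOVA (a mixed-model ANCOVA for secondary outcomes 2 and 6) to the change from baseline, and check the model itself: "Q-Q plots and residuals versus fitted values plots will be generated for the evaluation of the model adequacy". If that check fails, the dependent variable is transformed, by logarithm or otherwise. Both sections then list a two-sample t-test for between-group differences, followed by: "If the outcome is not normally distributed, then Wilcoxon rank sum test will be used". They do not say how the t-test or Wilcoxon result relates to the ANCOVA.

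**The concern.** Three things do not fit together.

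- **The trigger.** ANCOVA needs well-behaved residuals, not a normal raw variable. Raw values here may look non-normal because of selection. Entry requires "BMI from 25.0 to 29.9" kg/m², and percent fat pools men with a DXA floor of 20% and women with a floor of 30%. The protocol looks at the variable, the SAP looks at residuals for the ANCOVA, and the SAP looks at the outcome again for the t-test/Wilcoxon pair.
- **The log remedy.** The SAP's dependent variable is a change score. Changes in fat, weight or laboratory values can be zero or negative, and then have no logarithm. Protocol 12.3 instead puts the variable on the log scale, which works for positive values.
- **The fallback.** The one between-group rank test named discards the baseline value that both documents otherwise adjust for.

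At stake are some precision, the adjustment for chance baseline imbalance, and freedom to choose the test after seeing the data.

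**Working it through.** **Inputs.** From Protocol 12.1: "50 per group; 40 completers", "two-sided unadjusted 5% significance level, 80% power and 20% attrition rate", SD 1.19% and 1.24 kg, detectable differences 0.76% and 0.79 kg. Assumed, because the documents give neither: the baseline-change correlation r, and the laboratory distributions and baseline to week-12 correlations.

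**The plan's own figure.** A noncentral-t calculation with 40 per arm gives detectable differences of 0.755% and 0.787 kg, which round to the stated values. 40/(1 − 0.2) = 50 randomised per arm. The sample size reproduces.

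**Primary outcome, near-normal errors, 1.19% taken as the SD of raw change.**

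- ANCOVA power = Φ(0.76 / [1.19·√(1 − r²)·√(2/40)] − 1.96).
- Wilcoxon on change, relative efficiency 0.955: effective n = 40 × 0.955 = 38.2, so power = Φ(0.76 / [1.19·√(2/38.2)] − 1.96) = 79.7% at any r.

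| r | ANCOVA | Wilcoxon | Loss (points) |
|---|---|---|---|
| 0 | 81.5% | 79.7% | 1.8 |
| 0.3 | 84.9% | 79.7% | 5.2 |
| 0.5 | 91.0% | 79.7% | 11.2 (unrounded powers) |

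If 1.19% is already a residual SD, which the protocol does not say, the losses are 1.8, 5.6 and 13.9 points.

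**Rank ANCOVA against Wilcoxon on change**, simulated with 6,000 trials, 40 per arm and the same SD and difference:

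| Residuals | r = 0 | r = 0.3 | r = 0.5 |
|---|---|---|---|
| Normal | 77.5 v 77.7% | 82.2 v 78.8% | 87.4 v 78.3% |
| Skewed | 95.5 v 95.6% | 95.5 v 93.8% | 97.1 v 92.0% |
| t, 4 df | 89.9 v 90.2% | 91.6 v 88.0% | 94.3 v 86.2% |

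With normal residuals the gain from keeping baseline is −0.2, 3.4 and 9.1 points, that is about 0 to 9. In no cell does the unadjusted test win by more than simulation error.

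**Skewed laboratory variable** (log-normal, true 20% reduction, 40 per arm, 3,000 trials; correlation is baseline to week 12):

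| Log SD, correlation | Log-scale ANCOVA | Rank ANCOVA | Wilcoxon on raw change | Loss v rank | Loss v log |
|---|---|---|---|---|---|
| 0.5, 0.6 | 68% | 65% | 51% | 14 | 17 |
| 0.5, 0.7 | 79% | 74% | 61% | 13 | 18 |
| 0.5, 0.8 | 90% | 87% | 78% | 9 | 12 |
| 0.4, 0.7 | 93% | 89% | 81% | 8 | 12 |

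The standard error of one such power is at most √(0.5 × 0.5/3,000) = 0.9 point. A smaller run of the first row gave 66% against 49%, so these ranges are good to a few points. Rank ANCOVA held its type I error at 4.2 to 5.5% across runs.

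**The case against.** The other side has four good arguments.

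1. A reader might infer that Protocol 12.3 itself drops the covariate. It does not. It leaves the test unnamed, and a rank ANCOVA would satisfy its wording. The unadjusted Wilcoxon comes from the SAP.
2. A reader might take the laboratory losses as what the plan will incur. Under the protocol, log-normal variables go to the log scale and stay in a baseline-adjusted analysis. Only intractable cases reach the rank test. The losses in the last table arise only if the SAP rule is followed instead.
3. A reader might conclude that model assumptions go unchecked, or that the eligibility limits make a switch likely. The SAP does check residuals. Its Wilcoxon sentence most naturally replaces the t-test, not the ANCOVA. The checks are visual with a high bar, and the analysed variable is a change, which the BMI entry limits do not truncate.
4. When residuals are truly non-normal, Wilcoxon can beat ordinary ANCOVA: by 15.4, 10.3 and 3.1 points at r = 0, 0.3 and 0.5 with the skewed residuals simulated. A rank fallback is therefore reasonable in itself.

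The first three limit the point, and the fourth supports having a rank method. None explains why that method should omit baseline, and in the skewed case rank ANCOVA matched or beat Wilcoxon. The SAP also allows a transformation other than the logarithm, but names none that suits a change score, so its residual check cures the problem only in part.

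**Conclusion.** The point holds in a limited form. The two documents use different triggers, the SAP's log remedy can fail on change scores, and the only between-group rank test named is unadjusted. An adjusted analysis with acceptable residuals could thus be displaced by an unadjusted one, or stand beside it with no rule on which counts.

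The size is conditional. For the primary outcome with normal errors, Wilcoxon loses about 2 to 11 points against ANCOVA and about 0 to 9 against rank ANCOVA for r from 0 to 0.5. The first range reaches about 14 points if the stated SD is already a residual SD. With r near zero almost nothing is lost. For skewed laboratory variables the loss is about 8 to 14 points against rank ANCOVA and about 12 to 18 against log-scale ANCOVA, and only where the SAP rule overrides the protocol's log step. All correlations and laboratory distributions are assumptions. The sample size calculation is not in question. This is an inexpensive improvement, not a flaw that invalidates the analysis.

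**What to change.** Put the same rule in Protocol 12.3 and SAP 5.1 and 5.2:

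1. Fit the ANCOVA or mixed model first and judge normality on its residuals only.
2. For skewed positive variables, take logs of both the follow-up and the baseline value, not of the change. Using the difference of logs as the dependent variable, with log baseline as covariate, gives the same group estimate.
3. If residuals remain intractably non-normal, use a rank ANCOVA (ranks of follow-up on group and ranks of baseline) in place of the Wilcoxon rank sum.

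The cost is a few sentences before unblinding and no new data. The drawback is that rank ANCOVA gives a p-value without an estimate in original units, so report a descriptive estimate alongside it. The Wilcoxon p-value has the same limitation.

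### The mixed model for waist, hip, waist/hip ratio and bowel frequency names only a subject random effect; fitted as a plain random intercept, it miscalibrates the week-6 and week-12 tests whenever the two visit variances differ

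*Protocol*

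**What the plan says.** Protocol 12.3 sets the general rule: "Continuous secondary endpoints will be tested for between-group differences using repeated measures linear mixed-effects ANCOVA". It gives the reason in one sentence, "This will allow for the random effects associated with each subject to be accounted for", and then names the fixed effects (study group by visit) and the baseline value as covariate. The response is the change at each visit.

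SAP 5.2 narrows the scope to two outcome groups: "Continuous secondary outcomes #2 and # 6 will be assessed using linear mixed effects ANCOVA". These are #2 (waist, hip and their ratio) and #6 (bowel movement frequency), the two that are compared at both week 6 and week 12. For them the SAP lists fixed effects only: the model "will be assessed using linear mixed effects ANCOVA, the fixed effects will include the baseline measurements as covariate and group\*visit as the factor variables". Secondary outcomes #1, #3, #4 and #5 get a single-visit ANCOVA at week 12, as does the primary outcome (SAP 5.1).

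The SAP states separate null hypotheses by visit: H02.1 and H06.1 at week 6, H02.2 and H06.2 at week 12. Neither document states a residual covariance structure, whether variances may differ by visit, the form of the random effects, or a degrees-of-freedom method.

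**The concern.** A subject random effect deals with the correlation between a participant's two changes. It does not by itself let the two changes have different variances. In its commonest form (a random intercept plus independent residuals with one variance) it gives both visits the same total variance. Each visit contrast is then judged against a pooled variance, not its own.

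Because H02.1/H02.2 and H06.1/H06.2 are tested visit by visit, the mismatch reaches the reported p-values and confidence intervals directly. The visit with the larger spread has too high a false-positive rate and too narrow an interval. The other visit loses power.

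**Working it through.** **The plan's own figure.** Protocol 12.1 gives no calculation for outcomes #2 and #6; its figures are for the primary outcome. They are reproduced here only to fix the sample size used below. The section states "With a total sample size of 100 (50 per group; 40 completers" at a "two-sided unadjusted 5% significance level, 80% power and 20% attrition rate", for a difference in "mean change in percent body fat or body fat mass of 0.76% or 0.79 kg respectively" with "standard deviations of 1.19% and 1.24 kg for percent body fat and body fat mass respectively". With 40 per arm, the t-based detectable differences are 0.755% and 0.787 kg, which agree with the plan, and 40/0.8 = 50 randomised per arm. These figures do not bear on the present point.

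**Inputs.** Two post-baseline visits; a two-sided 5% test; equal arms. The ratio r = SD6/SD12 of the change scores is not in the documents, so it is an assumption and a range is shown.

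**Step 1: what a random intercept implies.** With intercept variance t² and residual variance s², the model variance of the change is t² + s² at both visits. Let V6 and V12 be the true variances and C the covariance. In balanced data the between-subject mean square estimates (V6 + V12 + 2C)/2 and the within-subject mean square estimates (V6 + V12 − 2C)/2. The estimate of t² + s² is half their sum, (V6 + V12)/2, which is the average of the two visit variances.

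**Step 2: standard error relative to the truth.**
- Week 12: sqrt[(V6 + V12)/(2·V12)] = sqrt[(1 + r²)/2] = k.
- Week 6: k/r.

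**Step 3: true level of a nominal 5% test** (normal approximation): 2·[1 − Φ(1.96 × SE ratio)]. For r = 0.8, k = sqrt(1.64/2) = 0.906, 1.96 × 0.906 = 1.775, and the level is 7.6%.

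| r = SD6/SD12 | SE ratio, week 12 | Type I, week 12 | SE ratio, week 6 | Type I, week 6 |
|---|---|---|---|---|
| 1.0 | 1.000 | 5.0% | 1.000 | 5.0% |
| 0.9 | 0.951 | 6.2% | 1.057 | 3.8% |
| 0.8 | 0.906 | 7.6% | 1.132 | 2.7% |
| 0.7 | 0.863 | 9.1% | 1.233 | 1.6% |
| 1.25 | 1.132 | 2.7% | 0.906 | 7.6% |

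The last row mirrors r = 0.8: if spread shrinks over time, week 6 is the inflated test.

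**Step 4: simulation.** Random-intercept model by REML, 40 per arm, correlation 0.7 between visits (assumed), 1000 runs per setting, compared with an ANCOVA on week 12 alone.

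| SD12/SD6 | Mean week-12 SE, model / visit-specific | Type I week 12, model | Type I week 12, ANCOVA | Type I week 6, model |
|---|---|---|---|---|
| 1.00 | 0.2236 / 0.2237 | 5.4% | 5.4% | 5.9% |
| 1.25 (r = 0.8) | 0.2525 / 0.2790 | 7.3% | 4.9% | 3.0% |
| 1.41 (r ≈ 0.71) | 0.2737 / 0.3160 | 8.3% | 5.6% | 1.7% |

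The SE ratios, 0.905 and 0.866, match the formula.

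**Step 5: effect of LOCF.** SAP 7 allows LOCF. Take V6 = 1, V12 = 2, and 20% of week-12 values carried forward from week 6. The week-12 variance becomes 0.8 × 2 + 0.2 × 1 = 1.8, the SE ratio is sqrt[(1 + 1.8)/(2 × 1.8)] = 0.88, and the level is about 8.4%, against 9.0% without LOCF. The effect shrinks slightly.

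**The case against.** The strongest reply is that the plan does not state the model that causes the problem. A reader might infer from Protocol 12.3 that equal variances are imposed. The documents do not support that: neither mentions a random intercept, compound symmetry or homogeneous residuals, the protocol speaks of random effects without giving their form, and a repeated-measures mixed model with visit-specific variances would also fit the text. This stands, and the point is therefore conditional on the usual fit.

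A reader might also infer that the week-12 test is inflated. That needs a larger spread at week 12 than at week 6, and no visit-specific SDs are given. Growth is not obvious here. Bowel frequency is a 7-day average taken in the same way before each time point, and repeat-measurement error in the circumferences enters at both visits. This also stands. What remains is that one of the two tests is miscalibrated whichever way the variances differ.

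Three further replies carry less weight.
- SAP 5.2 also lists a two-sample t-test, which would not pool across visits if run by visit. It is a second between-group p-value with no stated precedence, and it does not correct the mixed-model one.
- The planned Q-Q and residual-versus-fitted plots include no comparison of variance by visit, and the only stated remedy is transformation of the response.
- LOCF narrows the gap only slightly, and multiple imputation is the stated alternative to it.

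**Conclusion.** The point holds in conditional form. The plan names a subject random effect and nothing else for within-subject dependence. Under the usual random-intercept fit, the week-6 and week-12 tests for outcomes #2 and #6 are miscalibrated whenever the two variances differ.

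The size depends on an assumed SD ratio: small at 0.9 (6.2% against 5%), more noticeable at 0.7 (9.1%), nil at 1.0, and reversed in direction above 1.0. The figures assume balanced data and a normal approximation; the simulation adds an assumed correlation of 0.7.

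The reach is limited. The primary outcome and secondary outcomes #1, #3, #4 and #5 are not affected under the SAP. This is an inexpensive improvement to two secondary outcome groups, not a threat to the trial's main conclusion.

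**What to change.** In Protocol 12.3 and SAP 5.2, state that the week-6 and week-12 changes for outcomes #2 and #6 are modelled with an unstructured covariance across the two visits (a variance for each visit and a covariance), fitted by REML with Kenward-Roger or Satterthwaite degrees of freedom. The group contrasts at week 6 and week 12 should be taken from that model. A baseline-by-visit term is optional and is not needed to cure this problem.

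The cost is one sentence and one extra covariance parameter: three (two variances and a covariance) in place of two (intercept and residual variance). Either software package named in Protocol 12.3 can fit it. The unstructured model was not itself simulated. The week-12 ANCOVA, which also uses the visit's own variance, held 4.9% to 5.6% in the simulation above. The change protects both visits whichever has the larger spread.
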